8.1.3 Protocol Deviations

The number and percentage of subjects with one or more of the following major protocol deviations will be summarized overall as well as by category:

- Those who entered the study even though they did not satisfy the entry criteria. adherence to the inclusion and exclusion criteria will be the determining factor for this category of protocol deviations.
- Those who developed withdrawal criteria during the study but were not withdrawn. The only criterion defined in the protocol that required withdrawal from the study was the development of melanoma.

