11.1.3 Assessment for Melanoma

A comprehensive assessment for the presence of melanoma must be performed at yearly intervals, including at the Early Termination/End of Study, by a dermatologist experienced with the diagnosis of the condition. If a suspicious lesion is present, a biopsy should be obtained for proper diagnosis and subjects should be referred to appropriate follow-up treatment, if necessary. Subjects who have a melanoma present at the start of the study, or who develop a melanoma during the course of the study should be discontinued from participation and referred for proper follow-up care.

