11.1.4 Assessment of Impulsive Behavior

To monitor for the development of intense impulsive behavior, the Minnesota Impulsive Disorders Interview (MIDI) will be administered at 6 month intervals during the course of the subject's involvement in the study, and at the time of the subjects' termination from the study. In addition, the Investigator should ask the subjects to inform him/her immediately if they experience new or increased gambling urges, increased sexual urges, or other intense urges while taking LCIG.

If the subject's impulsivity is judged to be clinically significant, in the judgment of the Investigator, the subject will be discontinued from participation in the study and referred for appropriate follow-up care.

The General Information and Background Module sections of the MIDI do not need to be completed.

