11.1.5 Columbia-Suicide Severity Rating Scale (C-SSRS)

The Columbia-Suicide Severity Rating Scale (C-SSRS)¹⁶ is a systematically administered instrument developed to track suicidal adverse events across a treatment study. The instrument is designed to assess suicidal behavior and ideation, track and assess all suicidal events, as well as the lethality of attempts. Additional features assessed include frequency, duration, controllability, reason for ideation, and deterrents. The C-SSRS is considered a low-burden instrument, as it takes less than 5 minutes to administer. Raters will receive instruction on the administration of the C-SSRS assessment scales prior to administration of the scales. The C-SSRS will be administered at the times outlined in [Table 2](#).

Subjects expressing suicidal ideation with plan, either by answering "yes" to questions 4 and/or 5 to the suicidal ideation portion of the C-SSRS or via clinical interview, will be evaluated immediately by the Investigator or another medically qualified individual (M.D., D.O.). The Medical Monitor must be notified and the subject will be discontinued from participation in the study. The subject will be referred for appropriate psychiatric follow-up treatment, if necessary, per the judgment of the Investigator or the medically qualified individual. The Medical Monitor will also be notified. In addition, if the subject expresses suicidal ideation or suicidal behavior at any time during the course of the study, the subject should be discontinued from participation in the study and referred for proper psychiatric follow-up care. The Investigator and the Medical Monitor should be notified immediately as well.

Under no circumstances should a subject who has positively endorsed or expressed suicidal ideation or behavior be left alone, be allowed to exit the site, or go home before a qualified medical professional has evaluated the subject's risk.

The "Already Enrolled Subjects" C-SSRS will be the first assessment scale administered to the subject. At each subsequent assessment, the "Since Last Visit" C-SSRS scale should be administered.

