If the subject has previously completed the "Already Enrolled Subjects" scale in the S187.3.003 study, the subject should complete the "Since Last Visit" scale at all scheduled time points outlined in [Table 2](#) in this study. For subjects with a C-SSRS completed at their S187.3.003 final visit, that S187.3.003 final visit C-SSRS assessment will be considered baseline for the S187.3.005 study. For all other subjects, the first C-SSRS assessment completed in this study will serve as baseline.

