6.4.8 Visit Windowing Conventions

Assessments will be assigned to the Baseline Period if the date is on or before the Date of the First 3005 LCIG Infusion as defined in Section 6.4.1 and to the Post-Treatment Period if the date is after the end of the relevant Treatment Period as defined in Section 6.4.6.

Assignment of assessments to visits during the Treatment Period will use visit windows based on the day of the assessment relative to the Date of the First 3005 LCIG Infusion as described in Table 2 below.

Table 2. Visit Windowing Conventions

Visit Label	Target Visit Day	Study Day Range
Baseline	≤ 1	
Month 6	180	2 to 270
Month 12	360	271 to 450
Month 18	540	451 to 630
Month 24	720	631 to 810
Month 30	900	811 to 990
Month 36	1080	991 to 1170
Month 42	1260	1171 to 1350
Month 48	1440	1351 to 1530
Month 54	1620	1531 to 1710
Month 60	1800	1711 to 1890
Month 66	1980	1891 to 2070
Month 72	2160	2071 to 2250
Month 78	2340	2251 to 2430
Month 84	2520	> 2430

If a subject has two or more assessments in the same visit window, the assessment closest to the target visit day will be used. If two assessments are equidistant from the target visit day, the later assessment will be used.

Each reported post-baseline lab and vital sign measurement shall be evaluated to determine if it meets potentially clinically significant criteria. For all other analyses of

labs and vital signs, if two measurements are on the same date, the average will be calculated and treated as the value for that date.

6.4.9 3005 Treatment Year

The following events will be summarized by 3005 Treatment Year using the study day intervals described in [Table 3](#) below: premature study discontinuations, prevalence of concomitant anti-parkinsonian medication use, the incidence and prevalence of adverse events, the incidence of device complications, and the number of PEG tube and J-tube replacements.

Table 3. 3005 Treatment Year

3005 Treatment Year	Study Day Range
Year 1	2 to 365
Year 2	366 to 730
Year 3	731 to 1095
Year 4	1096 to 1460
Year 5	1461 to 1825
> Year 5	> 1825

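### SAP 8.1.3 calls melanoma the protocol's only withdrawal criterion; protocol 11.1.4 (impulsivity) and 11.1.5 (suicidality) set two more, which DVT001 and DVL001 would not show

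*SAP*

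**What the plan says.** SAP 8.1.3 counts two kinds of major deviation: entering the study without meeting the entry criteria, and meeting a withdrawal criterion without being withdrawn. It closes the second kind with a statement about the protocol: "The only criterion defined in the protocol that required withdrawal from the study was the development of melanoma". SAP 9.2 reports the result in DVT001 (number and percentage by category) and DVL001 (by-subject listing).

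The protocol gives discontinuation rules in three consecutive safety sections.

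- 11.1.3, melanoma: subjects "who develop a melanoma during the course of the study should be discontinued from participation and referred for proper follow-up care".
- 11.1.4, impulsive behavior: "If the subject's impulsivity is judged to be clinically significant, in the judgment of the Investigator, the subject will be discontinued from participation".
- 11.1.5, suicidality, in two grades. Ideation with a plan is identified by a yes to "questions 4 and/or 5 to the suicidal ideation portion of the C-SSRS or via clinical interview", and the consequence is: "The Medical Monitor must be notified and the subject will be discontinued from participation in the study". The wider grade reads: "if the subject expresses suicidal ideation or suicidal behavior at any time during the course of the study, the subject should be discontinued".

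**The concern.** The SAP sentence describes the protocol, and the description is wrong. It also does work in the analysis, because it fixes what the second deviation category can contain. Followed as written, a subject who reported suicidal ideation with a plan, or whose impulsivity was judged clinically significant, and who was nevertheless kept on LCIG would not appear in DVT001 or DVL001 unless an entry criterion had also been breached. Protocol 13.1 makes long-term safety the primary statistical objective. A reader of the clinical study report would expect the deviation table to show whether the suicidality rule was followed, and the SAP would tell that reader there was no such rule.

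**Working it through.** No sample size, power or error rate is involved, so the check is a comparison of texts.

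**1. Count the criteria.**

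| Criterion | Protocol | Verb | Named in SAP 8.1.3 |
|---|---|---|---|
| Melanoma | 11.1.3 | should | yes |
| Impulsivity judged clinically significant | 11.1.4 | will | no |
| Suicidality: ideation with plan | 11.1.5 | will | no |
| Suicidality: any ideation or behavior | 11.1.5 | should | no |

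By protocol section there are 3 criteria; 1 is named and 3 − 1 = 2 are omitted. Counting the two suicidality grades separately gives 4 triggers, of which 4 − 1 = 3 are omitted. I use two of three, since the grades are nested. I leave out the Investigator's six-monthly continuation decision (protocol 7.1), because that is itself the decision to stop, so it cannot be met and ignored in the same sense.

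**2. Can *required* explain the omission?** No. Melanoma carries the weaker verb, while both omitted criteria contain a *will*.

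**3. Did the rules come too late?** No. SAP 4.0 says the plan covers the protocol of 17 December 2013 with Global Amendments 1 to 4. Protocol 1.1 does not list 11.1.4 or 11.1.5 among the sections that amendment changed. SAP 8.5.5.5 itself records that the C-SSRS arrived with Amendment 3.

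**4. Is it repaired elsewhere?** No. SAP 8.5.5.6 repeats the melanoma rule. SAP 8.5.5.4 (MIDI) and 8.5.5.5 (C-SSRS) plan incidence summaries and state no discontinuation rule. SAP 10.1, which lists departures from the protocol, does not mention this.

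**5. How far does it reach?** SAP 8.1.1 defines the samples by consent, at least one infusion and at least one efficacy assessment, not by deviations. No sample changes, and neither do the efficacy, AE, MIDI or C-SSRS summaries. For C-SSRS answers in the Treatment Period, the omitted subjects cannot exceed those with any affirmative ideation or behavior answer in table 14.3__7.3. That bound does not cover suicidality found only by clinical interview, or impulsivity.

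**6. When did each rule apply?** The C-SSRS is absent from the Amendment 1 and 2 schedules (SAP 12.1.1, 12.1.2) and present from Amendment 3 (12.1.3). The MIDI and melanoma checks are already in the Amendment 1 schedule. The documents do not say when each discontinuation rule was first written.

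**7. Which C-SSRS answers are on-study?** For subjects without a C-SSRS at their S187.3.003 final visit, protocol 11.1.5 says: "For all other subjects, the first C-SSRS assessment completed in this study will serve as baseline". The SAP sorts by date instead: "Assessments will be assigned to the Baseline Period if the date is on or before the Date of the First 3005 LCIG Infusion". For a subject already on 3005 drug when the C-SSRS was introduced, the first form is therefore baseline by one rule and Treatment Period by the other. The documents do not show what that form asks, so they do not settle how much of it concerns events before the study.

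**The case against.** The best case on the other side is that little follows from the error. This is a single-arm study with no alpha level (protocol 13.4), nobody is excluded for a deviation, and C-SSRS and MIDI results are tabulated and listed anyway. That stands, and it limits the weight of the point. It does not make the sentence true or put the missing subjects into the deviation outputs.

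Four stronger readings are tempting, and the documents do not support them.

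- *Subjects were kept on in breach of the protocol.* The documents contain no data on this.
- *Impulsivity breaches could not be traced at all.* QSL009 gives MIDI answers and the screen result, not the Investigator's judgment. But AEL001 lists all adverse events, SAP 8.5.1 collects severity, action taken and whether the event led to termination, and CBL001 lists the continued-benefit determinations. None of these is the formal 11.1.4 judgment, but together they offer a partial route. For suicidality, QSL010 can be set against DSL002 by hand.
- *Only ideation questions 4 and 5 can meet the* will *grade, so other positive items belong in the lower one.* Protocol 11.1.5 also allows the *will* rule to be met by clinical interview. C-SSRS answers alone cannot place those subjects in the lower grade.
- *The share of C-SSRS items involved measures the size of the problem.* It counts questions, not subjects.

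Two practical objections also stand. A count that ignored effective dates could report deviations from a rule not yet in force. And the protocol gives no interval after which a subject counts as not withdrawn.

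**Conclusion.** The point holds. SAP 8.1.3 misstates the protocol and leaves two of three withdrawal criteria out of the category that is meant to capture them. The consequence is confined to DVT001 and DVL001. The number of subjects affected is unknown and may be zero, and nothing here bears on the validity of the efficacy or other safety results. It should be corrected because the sentence is plainly wrong, the SAP also governs the final study report, and correction is cheap. The count of three rests on treating each protocol section as one criterion. Dating the suicidality rule from Amendment 3 assumes that it arrived with the C-SSRS, which is likely but not stated.

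**What to change.** Delete the sentence and name three criteria in SAP 8.1.3, each applied only from the date on which the amendment that introduced it took effect: melanoma (protocol 11.1.3), clinically significant impulsivity (11.1.4) and suicidality (11.1.5).

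- **Suicidality:** use on-study C-SSRS responses and recorded AEs, compared with disposition dates. Put a yes to ideation question 4 or 5 on its own line, and do not label the remaining positives as lower grade. State how the first on-study C-SSRS is handled.
- **Impulsivity:** use a recorded Investigator judgment or AE. A positive MIDI screen alone is not the protocol's trigger.
- **Reporting:** state the interval between trigger and discontinuation that counts as not withdrawn, report DVT001 by criterion, and footnote any criterion that the collected data cannot assess. The documents name no field for the Investigator's impulsivity judgment or for suicidality found at interview, so those parts may end as footnotes.

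The cost is revised SAP wording and a small cross-check of data already held. The deviation count may rise.

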The final visit in the previous open-label LCIG study will provide baseline assessments for the S1878.3.005 study. Subjects will be reassessed every 6 months for the appropriateness of the continuation of treatment with LCIG. If the subject is deemed inappropriate for continued treatment by the Investigator, the subject would be discontinued from treatment and the PEG-J will be removed, with a follow-up visit

occurring 1 week later. For subjects who elect not to continue LCIG treatment, the PEG-J will be removed, and a follow-up clinic visit will occur 1 week later.

Safety assessments should include physical examination, neurological exam, orthostatic vital signs, weight, adverse event monitoring, assessment of impulsive behavior and sleep attacks, melanoma check, electrocardiogram (ECG), clinical hematology, biochemistry, special labs to monitor for vitamin deficiencies, and urinalysis.

The following efficacy assessments will be completed at US sites:

- Parkinson's Disease Diary[®] assessment of motor state completed for the 3 consecutive days prior to each clinic visit (excluding the drug dispensation visits),
- Unified Parkinson's Disease Rating Scale (UPDRS), and
- Parkinson's Disease Questionnaire-39 (PDQ-39).

At each visit, complications or adverse events with the infusion device (i.e., the tubing system and the pump) will also be recorded and reported. Tube placement will be checked by radiography if there is a clinical indication that the tube has been displaced. The tube will be repositioned, if needed, to the original placement site just beyond the ligament of Treitz. At each visit the tube insertion site, including the stoma, will also be inspected. On a yearly basis, at a minimum, an assessment will be made of the need for a replacement of the PEG-J. The frequency of replacement should be in accordance with local practice.

The protocol duration is planned until the finished product is available commercially in the respective countries where subjects are participating in the study. The expected protocol duration will continue through successful NDA and subsequent approval (approximately 4 years). ***The protocol duration will be extended 4 years in the UK from the approval date of Amendment 3.01. If it is deemed necessary to continue treatment after 4 years in the UK, either an amendment to the current protocol will be made or a new protocol will be submitted.***

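### SAP 8.1.3 names melanoma as the only withdrawal criterion, but the protocol also directs discontinuation for suicidality and for impulsivity judged clinically significant

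*SAP*

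**What the plan says.** SAP 8.1.3 sets up two kinds of major protocol deviation: entry despite failing the entry criteria, and remaining on study after meeting a withdrawal criterion. For the second kind it gives a single operational rule: "The only criterion defined in the protocol that required withdrawal from the study was the development of melanoma". SAP 9.2 reports these deviations as a count (DVT001) and a by-subject listing (DVL001).

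The protocol ties discontinuation to a specific finding in three places.

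- Protocol 11.1.3, melanoma: subjects who "develop a melanoma during the course of the study should be discontinued from participation".
- Protocol 11.1.5, suicidality. For ideation with a plan, shown by C-SSRS ideation questions 4 or 5 or at interview: "The Medical Monitor must be notified and the subject will be discontinued from participation in the study". For ideation or behavior more generally: "In addition, if the subject expresses suicidal ideation or suicidal behavior at any time during the course of the study, the subject should be discontinued".
- Protocol 11.1.4, impulsivity: where "impulsivity is judged to be clinically significant, in the judgment of the Investigator, the subject will be discontinued from participation in the study".

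**The concern.** The SAP sentence is a factual statement about the protocol, and it also defines what the programmers will look for. If it is wrong, the category is too narrow, and the reader is told that it is complete.

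The omitted rules protect subjects. Someone reading DVT001 in the study report could take an empty row as evidence that every mandatory-withdrawal rule was respected, when compliance with the suicidality and impulsivity rules had not been examined. Protocol 13.1 makes long-term safety the primary statistical objective, so adherence to safety-driven stopping rules should be reported correctly even in a descriptive table.

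**Working it through.** No arithmetic beyond a count is involved. The check is a comparison of texts.

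1. **Strength of wording.** The melanoma rule says that subjects should be discontinued, and the SAP treats that as a requirement. The general suicidality rule uses the same verb. The ideation-with-plan rule and the impulsivity rule say that the subject will be discontinued, which is firmer. No reading of the verbs keeps melanoma and drops the other two.

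2. **Count.** There are three event-based domains: melanoma, suicidality and impulsivity. The SAP names one, so 3 − 1 = 2 are omitted. If the two suicidality rules are counted separately, there are four rules and three are omitted. The conclusion is the same.

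3. **Other candidate rules.** Protocol 7.1 provides that if the subject is "deemed inappropriate for continued treatment by the Investigator, the subject would be discontinued from treatment". That is the decision to stop, not an event that triggers it, so it is not counted. Protocol 9.0 defines reasons for termination, and 10.8 lists medications that are not permitted. Neither directs withdrawal on a specific finding.

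4. **Protocol version.** SAP 4.0 says that it covers Global Amendments 1 to 4. SAP 8.5.5.5 records that the C-SSRS came in with Amendment 3, and the MIDI is already in the Amendment 1 schedule (SAP 12.1.1). The Amendment 4 change list in Protocol Appendix B shows no change to 11.1.4 or 11.1.5. The SAP was therefore not written against a protocol that lacked these rules.

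5. **Declared departure.** SAP 10.1 lists two changes from the protocol, the efficacy baseline and the grouping of adverse events of special interest. Neither concerns withdrawal.

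6. **Effect on outputs.** Take a subject who reports suicidal ideation at a 6-monthly visit and continues on LCIG. The response appears in the C-SSRS summary (QST003 in SAP 9.11.5) and listing (QSL010). The subject is not in the discontinuation listing DSL002, because no discontinuation occurred. On this ground the subject is not in DVT001 or DVL001 either, because suicidality is not a listed criterion. No output classifies the subject as retained against a rule.

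7. **What the data can support.** For suicidality, C-SSRS responses are collected at scheduled visits, but they do not capture every trigger. The ideation-with-plan rule also applies where the finding is made "or via clinical interview, will be evaluated immediately by the Investigator or another medically qualified individual". For impulsivity, a positive MIDI screen under SAP 8.5.5.4 is an algorithm applied to answers, whereas the protocol's trigger is the Investigator's judgment. Neither document describes a field that records that judgment.

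8. **The first on-study C-SSRS.** For subjects without a final-visit C-SSRS in S187.3.003, the protocol says: "For all other subjects, the first C-SSRS assessment completed in this study will serve as baseline". That designates a reference assessment. It does not suspend the discontinuation rule, which applies throughout the study. Ideation during Study 3005 reported at that first assessment still counts. Only a response that refers solely to the time before Study 3005 falls outside the rule.

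**The case against.** The strongest reply is that little depends on this sentence. No subject sample in SAP 8.1.1 is defined by deviations, so no denominator or estimate changes. C-SSRS and MIDI results are tabulated and listed by subject and visit, and discontinuations are listed with the last infusion day. A careful reader could find a retained subject by cross-matching. The impulsivity rule cannot be programmed from any field that the documents describe, so leaving it out of an automated category is understandable.

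Most of this stands. It limits the point to a minor correction and makes impulsivity secondary to suicidality. It does not rescue the sentence. The SAP does not say that the other rules were set aside as hard to program; it says that they do not exist. The listings hold the ingredients for a check, but a reader told that melanoma was the only criterion has no reason to carry it out.

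Three stronger readings are tempting. A reader might infer that subjects were in fact kept on treatment after suicidal ideation; the documents give no C-SSRS or MIDI incidence and no retention data, so this cannot be said. A reader might infer that safety results are understated; the safety tables do not depend on the deviation category. A reader might treat every positive MIDI screen in a continuing subject as a deviation; Protocol 11.1.4 turns on clinical judgment, so a screen alone is not one.

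**Conclusion.** This is a SAP–protocol inconsistency of minor severity. The statement in SAP 8.1.3 is incorrect, and the retained-despite-criterion category built on it covers one of three event-based rules. A zero in that category would be uninformative about the suicidality and impulsivity rules.

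The number of subjects missed is unknown, and it is zero if sites followed Protocol 11.1.4 and 11.1.5. Only the descriptive deviation count and its listing can change. The conclusion rests on two assumptions: that a direction that subjects should be discontinued is a requirement, which is how the SAP itself reads the melanoma rule, and that DVT001 and DVL001 are produced as 8.1.3 defines them.

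**What to change.** Replace the sentence in SAP 8.1.3 with three criteria: melanoma (Protocol 11.1.3), suicidal ideation or behavior (11.1.5), and impulsivity judged clinically significant by the Investigator (11.1.4). Then specify how cases are found.

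- **Suicidality candidates:** any C-SSRS response showing ideation or behavior during Study 3005, including the first on-study assessment and excluding only responses that refer solely to the period before Study 3005; also suicidality reported as an adverse event or found at interview.
- **Impulsivity candidates:** positive MIDI screens and impulsivity adverse events, used only to nominate subjects for review.
- **Retention:** compare the event date with the discontinuation and last-administration dates on the DS panel, using DA dispensing dates as a supplement. Dispensing alone is an imperfect sign that a subject stayed on treatment.
- **Confirmation:** medical review of every candidate before a major deviation is counted.

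The cost is one corrected sentence, a small case review and possibly some site queries, chiefly to establish the Investigator's judgment on impulsivity. No protocol change is needed. The reported number of major deviations may rise.
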